2. 6-minute walk-test: this is a relatively easily performed test, evaluating the distance that a patient is able to walk within 6 minutes, in standard conditions (29, 30). This test is commonly used in studies evaluating functional status of patients with heart failure, and is an independent prognostic measure for these patients (30).

Study sample size and sample size and structure justification

Outcome: All-cause mortality at 12 months

From the paper by Roccaforte et al (16), we assume that the odds ratio is 0.80. We assume that 18% of usual care patients will die within the first 12 months.

The statistical power for detecting a significant difference at the 5% level (two-tailed test) is:

- For 600 patients in the usual care and 600 in the experimental care group: 32%
- For 400 patients in the usual care and 800 in the experimental care group: 30%

Conclusion:

There is not sufficient statistical power to include this outcome as one of the major endpoints of interest.

Approximately 4500 patients would be required to study this outcome with sufficient statistical power.

Randomization in a 2:1 ratio instead of 1:1 ratio is equivalent to reducing the sample size by about 13%.

Outcome: Re-hospitalization for heart disease at 12 months

From the paper by Roccaforte et al (16), we assume that the odds ratio is either 0.58 (their point estimate) or 0.67 (their upper 95% confidence limit). We assume that 33% of usual care patients will be re-hospitalized for heart disease within the first 12 months.

The statistical power for detecting a significant difference at the 5% level (two-tailed test), when the odds ratio is 0.58 is:

- For 600 patients in the usual care and 600 in the experimental care group: 99%
- For 400 patients in the usual care and 800 in the experimental care group: 98%

The statistical power for detecting a significant difference at the 5% level (two-tailed test), when the odds ratio is 0.67 is:

- For 600 patients in the usual care and 600 in the experimental care group: 89%
- For 400 patients in the usual care and 800 in the experimental care group: 85%

Conclusion:

There is sufficient statistical power to include this outcome as one of the major endpoints of interest.

Randomization in a 2:1 ratio instead of 1:1 ratio loses some power, but still provides acceptable power for this sample size.

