LDL-cholesterol**	_ _ / _ _ _ _	_ _ mg/dL
HDL-cholesterol**	_ _ / _ _ _ _	_ _ mg/dL
Triglycerides**	_ _ / _ _ _ _	_ _ mg/dL
FT4**	_ _ / _ _ _ _	_ . _ mcg/dL
TSH**	_ _ / _ _ _ _	_ _ . _ mU/mL
Vit B12**	_ _ / _ _ _ _	_ _ pg/mL
Folic Acid**	_ _ / _ _ _ _	_ _ . _ ng/mL
Iron**	_ _ / _ _ _ _	_ _ mcg/dL

*-For diabetic patients only

**-Once a year

Six minute walk test: meter. (Write '000' if not tested; specify the reason for the missing measurement:)

for the missing measurement:)

Resting ECG:

Date of test: - -

Findings:

1. QRS width mm

Findings (mark  where appropriate)	No	Yes
2. LBBB		
3. RBBB		
4. Atrial fibrillation		
5. Pathological Q waves that indicate old MI		

Was the patient given an implantable device within the last 6 months?

- a. **VVI** pacemaker;
- b. Atrial-ventricular pacemaker; **DDD**
- c. Biventricular pacemaker; **CRT**
- d. Biventricular pacemaker and defibrillator (**CRTD**)
- e. Defibrillator without pacing (**ICD**)
- f. No defibrillator or pacemaker

VII. Clinical evaluation summary and assessment of heart failure severity:

1. Heart failure stage* (mark the appropriate answer)
 - C. Structural heart disease with prior or current symptoms of HF
 - D. Refractory HF requiring specialized interventions

*-Source: Hunt SA, Abraham WT, Chin MH, et al. American College of Cardiology; American Heart Association Task Force on Practice Guidelines; American College of Chest Physicians; International Society for Heart and Lung Transplantation; Heart Rhythm Society. ACC/AHA 2005 Guideline Update for the Diagnosis and Management of Chronic Heart Failure in the Adult: a report of the American College of Cardiology/American Heart Association Task Force on Practice Guidelines (Writing Committee to Update the 2001 Guidelines for the Evaluation and Management of Heart Failure): developed in collaboration with the American College of Chest Physicians and the International Society for Heart and Lung Transplantation: endorsed by the Heart Rhythm Society. *Circulation*, 2005;112(12):e154-235.

2. NYHA functional classification* (mark the appropriate answer)
 - I. No limitations of physical activity. No heart failure symptoms;

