2 HANDLING OF MISSING DATA

Missing covariate data will be handled as far as possible by the method of multiple imputation (Little and Rubin, 2002).

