3 SUBJECT WITHDRAWALS DUE TO EARLY TERMINATION

Subjects will be censored at the time of last available information, if the endpoint of interest or any competing risk endpoints have not yet occurred.

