4.2 Secondary Efficacy Endpoints (events are counted until 31/7/12, ignoring early termination)

The arms will be compared with regard to:

1. Mortality from any reason
2. Hospitalization due to HF
3. Total days of hospitalization and total number of hospital admissions due to HF
4. Total days of hospitalization and total number of hospital admissions due to acute exacerbation of HF
5. Total days of hospitalization and total number of hospital admissions due to HF complications(including HF treatment adverse effects)
6. Total days of hospitalization and number of hospital admissions for any cause
7. Functional impairment (NYHA class) at 6 month intervals until the end of follow-up or end of trial
8. 6-minute walk test at 6 month intervals until the end of follow-up or end of trial
9. Quality of life (SF36 and VAS) at 6 month intervals until the end of follow-up or end of trial
10. Depression (PhQ9) adjusted for baseline value (subgroup with baseline value) at 6 month intervals until the end of follow-up or end of trial
11. BNP since 2009 adjusted for baseline value (subgroup with baseline value) at 6 month intervals until the end of follow-up or end of trial
12. Adherence to guidelines for recommended medical treatment

13. Total cost for health care provider to all health care services supplied to the disease management program (not including cost of disease management manpower and infrastructure designated for the study disease program)
14. Total cost of disease management at 6 month intervals until the end of follow-up or end of trial

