- 5. Regression with total days of hospitalization and total number of hospital admissions due to HF complications (including HF treatment adverse effects)
- 6. Regression with total days of hospitalization and number of hospital admissions for any cause
- 7. Functional impairment (NYHA class) at 6 month intervals
- 8. 6-minute walk test at 6 month intervals (in whole meters including zeros, probably will be categorized).

The 8th and 9th secondary endpoints are ordered outcomes. Therefore the proportional odds model using the GEE method implemented in the Genmod procedure (SAS 9.2), with repeated measurements, will be fitted. The proportional odds assumption will be tested and if violated a partial proportional odds model will be fitted.

- 9. Quality of life
SF36 at 6 month intervals – (score in 2 major domains (physical, mental)) – the GEE method implemented in the Genmod procedure (SAS 9.2), with repeated statement, will be fitted. If the data appear continuous then we will use GEE for a continuous outcome; if there are clumps of measurements (at 0 or 100 say), then we will categorize the data and use the proportional odds model version of GEE.
- 10. Regression model with repeated measures for Depression (PhQ9) at 6 month intervals adjusted for baseline value (subgroup with baseline value)
- 11. Regression model with repeated measures for BNP since 2009 at 6 month intervals, adjusted for baseline value (subgroup with baseline value).
- 12. Adherence to guidelines for recommended medical treatment. Two types of medical treatments will be considered: ACE-I/ARB's and Beta-blockers. We will examine adherence to each individual type and to their combination. Adherence to their combination will be scored 0,1 or 2 for patients who do not take any of the two types, patients taking only one type and patients taking both types of medicine, respectively. The two arms will be compared at 6 month intervals for their adherence to medical treatment using the proportional odds model or the partial proportional odds model using the Genmod procedure (SAS 9.2) with repeated statement.

Statistical Analysis Plan

13. A separate analysis will be conducted on the total cost for health care provider to all health care services supplied to the disease management program (not including cost of disease management manpower and infrastructure designated for the study disease program).

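### The six-monthly NYHA, walk, SF-36 and adherence outcomes have no missing-outcome rule, so the planned GEE can be biased, in either direction, if missed visits depend on earlier scores and differ by arm

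*Supplement*

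**What the plan says.** SAP 7.2.2 gives the model for the ordered outcomes: "the GEE method implemented in the Genmod procedure (SAS 9.2), with repeated measurements, will be fitted". It calls these the 8th and 9th endpoints, but in its own list NYHA is item 7 and walk is item 8. SF-36 (item 9) has its own paragraph, so I read this as a numbering slip that means NYHA and walk. For SF-36: "If the data appear continuous then we will use GEE for a continuous outcome"; otherwise the scores are categorised and fitted by proportional odds. Adherence (item 12) uses the same SAS procedure with repeated measures. All are adjusted for sex, age group, centre and baseline NYHA. Only items 10 (PHQ-9) and 11 (BNP) are also adjusted for their own baseline value, and these two are described as repeated-measures regression, not as GEE.

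The missing-data rule, SAP Section 2, is one sentence: "Missing covariate data will be handled as far as possible by the method of multiple imputation". SAP Section 3 covers withdrawal: "Subjects will be censored at the time of last available information".

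The measurement window in SAP 4.2 is, for example, "Functional impairment (NYHA class) at 6 month intervals until the end of follow-up or end of trial". For the walk test, SAP 7.2.2 has "6-minute walk test at 6 month intervals (in whole meters including zeros, probably will be categorized", and the follow-up form (Protocol Appendix E) has "Write '000' if not tested".

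**The concern.** Standard GEE without weights uses the visits that were recorded. That is how the method behaves by default; the SAP does not say so in words. The estimate is valid if, given the model covariates, whether a visit is recorded is unrelated to the outcome, including the patient's own earlier values. Four baseline covariates are unlikely to secure this for SF-36 and walk, whose own baseline is not in the model.

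Unequal attendance is plausible. The trial is open-label, follow-up runs from 1 to 5 years, and these outcomes are collected at heart failure centre visits. Only the programme arm has regular nurse contact between visits (SAP 1.6; Protocol, control-group care). Functional status and quality of life are stated objectives and hypotheses of the protocol, and these are the analyses that answer them.

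**Working it through.** **1. Is there a rule elsewhere?**
- SAP Section 2: covariates only.
- SAP Section 3: censoring, which serves the Cox models and has no meaning for a repeated score.
- SAP Section 6: intention to treat, defined only as analysis by assigned arm.
- SAP 4.2: events are counted to 31 July 2012 regardless of early termination, but visit-based scores stop at the end of follow-up.
- SAP 1.10: says visits were held for all randomized patients. That describes the schedule in both arms and cannot mean full attendance in a trial that expects deaths.
- Walk zeros: keep patients who attend but are not tested. They do not cover absentees, and they merge not tested with 0 metres.

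I found no missingness assumption, imputation, weighting or sensitivity analysis for these outcomes.

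**2. Mortality inputs.** The plan gives no figure for these endpoints, so there is none to reproduce. The sample-size section supplies mortality: "We assume that 18% of usual care patients will die within the first 12 months", with an odds ratio of 0.80.
- Odds: 0.18/0.82 = 0.2195; times 0.80 = 0.1756; 0.1756/1.1756 = 14.9% in the programme arm.
- Check of these inputs: total N for 80% power is 4,604, against the protocol's approximate 4,500. Power at 600 per arm is 29.8%, against the stated 32%. That gap does not bear on this point.
- With 1,360 analysed, assumed 680 per arm: about 122 v 102 deaths by year 1.
- Year 2, if the hazard stays constant (an assumption): 1 - 0.82² = 33% v 1 - 0.851² = 28%.

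**3. Bias with no true effect on the score.** Assumed settings:
- 1,360 patients and four six-monthly visits.
- Patient effect SD 7 plus visit noise SD 7, so total SD = √98 = 9.9.
- The log-odds of death and of permanent non-attendance rise by 0.8 for each 10 points worse on the previous value.
- Six-month death probability at an average score: 1 - 0.82^0.5 = 9.4% (control) and 1 - 0.851^0.5 = 7.8% (programme).
- Independence GEE on recorded visits, with arm and visit but no baseline covariates; 1,000 runs.

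| Control v programme | Missing at 24 months | Bias (points) | Type I error |
|---|---|---|---|
| Equal death | 39% v 39% | -0.01 | 5.1% |
| Death 18% v 14.9% per year | 39% v 34% | -0.14 | 6.1% |
| Same, plus 5% non-attendance per visit in both arms | 52% v 48% | -0.13 | 7.1% |
| Same deaths, non-attendance 10% v 5% | 61% v 48% | -0.50 | 18.4% |
| Equal death, non-attendance 10% v 5% | 61% v 51% | -0.34 | 9.9% |

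The Monte Carlo standard error at 5% is √(0.05 × 0.95/1,000) = 0.7 percentage points, so 6.1% is not clearly above nominal.

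**4. Effect of the planned covariate.** A second scenario held missingness at about 42% by month 24 in both arms (SD 10, intraclass correlation 0.6). Dropout was tied more strongly to the previous score in controls: log-odds slopes of 0.8 v 0.3, or 1.0 v 0.2.
- With a NYHA-like baseline covariate of assumed strength, the month-24 bias was -0.9 and -1.3 points under an independence working correlation, and -0.15 and -0.28 under an exchangeable one.
- With equal slopes (0.6 in both arms) it was about 0.
- A further run with arm-different dropout and such a covariate gave -1.2 to -1.7 points, and about 0 once missing scores were imputed from earlier visits.

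The score has no treatment effect here, so exchanging the arms' dropout settings reverses the sign.

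**The case against.** The strongest reply is that a gap in the text is not a demonstrated bias. With equal loss the bias is near zero, and the protocol's mortality difference alone moves a score of SD about 10 by only 0.14 points. The larger figures need attendance, or its link to health, to differ by arm, and no document gives such rates. Control patients also see a centre cardiologist every six months, the same data are collected in both arms, and stable programme patients are managed by the call centre. The SAP names no working correlation, so the independence results may overstate the bias for continuous SF-36. All of this stands, and it limits what can be said about size.

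It is also true that deaths are not lost to the trial: they count in the primary composite and have their own secondary analysis. Comparing function among survivors beside that analysis is a legitimate target. What remains open is the SAP's silence on whether this is the target, and on missed visits by living patients.

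Three stronger readings are tempting and not supported.
- That the programme will look worse: the sign follows from which arm is assumed to lose its sicker patients.
- That a majority of controls are dead by the five-year visit: the 18% is a first-year rate. With first recruitment in August 2007 and the study ending on 31 July 2012, almost nobody could reach year 5. Under uniform recruitment over 47 months, about 24/47 = 51% could reach year 3.
- That death must be ranked as the worst category: that is a different estimand, and a matter of choice.

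**Conclusion.** The point holds for items 7-9 and 12, as a cheap improvement to secondary analyses. The plan rests them on a stronger missingness assumption than necessary and does not state it. Bias needs two conditions together: attendance tied to earlier scores, and a difference between arms in the amount or strength of that loss. Under the assumptions tried, the overall bias ran from about 0 to -0.50 points, and the month-24 bias reached -1.7 points in the most unequal scenarios, on a score with SD about 10. These are illustrations, not estimates for this trial. For items 10 and 11 the missing-outcome rule is equally absent, but the GEE criticism does not apply as written. The primary analysis is not touched.

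**What to change.** - Extend SAP Section 2 to outcomes. For patients alive at the scheduled visit, multiply impute missing six-monthly NYHA, walk and SF-36 values, and PHQ-9 (item 10), from arm, baseline value and earlier visits, then fit the planned GEE. A likelihood mixed model is an alternative for continuous scores. Say whether items 11 and 12 follow the same rule.
- Adjust walk and SF-36 for their own baseline, as items 10 and 11 already do.
- Name the working correlation, and correct the 8th/9th numbering.
- Before imputing walk distance, separate a true 0 from 000 for not tested; the form already asks for the reason.
- State that these comparisons are among survivors and are read beside the mortality analysis. Ranking death as the worst category can be an optional sensitivity analysis.

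The cost is SAP wording and some extra programming. The result then relies on missing at random, which could itself fail but asks less than the present assumption. No new data are needed.
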